#### **4.1.3 Infectious prophylaxis for Pneumocystis Jiroveci**

As mentioned in Section [1.2.6.2.1.2](#), patients with MZL who received obinutuzumab based therapy had a higher rate of Grade 3-5 AEs compared to patients with FL, including a higher rate of infections. All adult subjects with MZL will receive prophylaxis for Pneumocystis Jiroveci during study therapy administration. Trimethoprim/sulfamethoxazole 1 DS tablet by mouth on Monday, Wednesday, and Friday is the preferred schedule. Subjects allergic to either component may receive inhaled pentamidine 300 mg once a month or other standard treatments.

Prophylaxis will begin with initiation of treatment (Cycle 1, Day 1 of dose-finding or Cycle -2, Day 1 of dose expansion) and will be stopped upon completion of therapy unless continued administration beyond this point is deemed necessary based on inadequate immune reconstitution. The use of antibiotics and/or anti-viral prophylaxis according to institutional guidelines is also allowed.

### **4.2 PROHIBITED FOOD AND MEDICATIONS**

Patients are prohibited from receiving the following therapies during treatment on this trial:

- Any therapies intended for the treatment of lymphoma/leukemia whether FDA approved or experimental (outside of this study)
- Immunosuppressive therapy
- Radiation therapy. **NOTE:** Radiation therapy to a symptomatic solitary lesion may be allowed at the investigator's discretion.
- Steroid treatment with doses higher than 20 mg of prednisone or equivalent for prolonged duration is not allowed. Short term treatment with high dose steroids for non-neoplastic intent (e.g., COPD) is allowed. If a patient is on chronic corticosteroid therapy, corticosteroids should be de-escalated to the maximum allowed dose after the patient has signed the IC. Patients may be using topical or inhaled corticosteroids.
- Strong CYP3A4 inhibitors around initiation of venetoclax as mentioned below in Section [4.2.1.1](#).
- Strong CYP3A inducers with venetoclax (Section [4.2.1.2](#))
- Prohibited food: Use of the following foods is prohibited for at least 3 days prior to initiation of venetoclax treatment and throughout venetoclax administration. Constituents of these foods have been shown to inhibit CYP3A4, the major enzyme responsible for the metabolism of venetoclax. Consumption of these foods could lead to increased venetoclax exposure:
  - Grapefruit
  - Grapefruit products
  - Seville oranges (included marmalade containing Seville oranges)
  - Star fruit

It is not possible to produce an exhaustive list of medications that fall into these categories, so if in question, refer to the appropriate product label.

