#### **3.7.1 30-Day Safety Follow-Up visit**

The mandatory Safety Follow-Up visit should be performed approximately 30 days following the last dose of study drug or before the first dose of new anti-cancer therapy, whichever comes first. Refer to the Study Calendar ([Appendix G](#)) for all tests and procedures to be conducted upon discontinuation of treatment and during follow-up. All AEs that occur prior to the safety follow-up visit should be recorded. See section [6.1.1](#) for documentation of AEs after study treatment has ended. The investigator or qualified designee will collect information about the new anti-neoplastic therapy initiated after the last dose of trial treatment. Once new anti-cancer therapy has been initiated the subject will move into survival follow-up.

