### 6.3.6 Definitions

#### 6.3.6.1 Best Overall Response

The best overall response rate (ORR) is the best response recorded from the start of the treatment until disease progression/recurrence (taking as reference for progressive disease the smallest measurements recorded since the treatment started).

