#### 6.3.6.2 Duration of Response

The duration of response (DOR) is measured from the time measurement criteria are met for CR or PR (whichever is first recorded) until the first date that recurrent or progressive disease is objectively documented (taking as reference for progressive disease the smallest measurements recorded since the treatment started), death, or, in the absence of PD, date of last assessment.

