#### 6.3.6.4 Event-Free Survival

Event-free survival (EFS) is defined as the duration of time from the date of study enrollment until time of disease relapse, disease progression, alternative anti-lymphoma therapy including radiation, or death, whichever occurs first.

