#### 6.3.6.6 Complete Response Rate

The proportion of patients who achieve a PET-negative complete response (CR) in accordance with the 2014 Lugano classification of the International Working Group Criteria for Non-Hodgkin's Lymphoma([125](#)) or International Workshop Group on CLL (iwCLL) criteria.

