### 6.3.6.8 Objective Tumor Response Rate

The proportion of patients who achieve at least a partial response (PR) to therapy.

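### Radiation to a single lesion is permitted on treatment, but best response, ORR, CR rate, DOR and PFS have no rule for it, so shrinkage of a decisive irradiated lesion is credited to the triplet

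*Combined protocol and SAP*

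**What the plan says.** Section 4.2 lists radiation among the therapies prohibited during treatment, then qualifies it: "Radiation therapy to a symptomatic solitary lesion may be allowed at the investigator's discretion".

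Section 6.3.6 defines the efficacy endpoints:

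- Best overall response (6.3.6.1) "is the best response recorded from the start of the treatment until disease progression/recurrence".
- CR rate (6.3.6.6) is "The proportion of patients who achieve a PET-negative complete response (CR) in accordance with the 2014 Lugano classification", or by the iwCLL criteria.
- Objective response rate (6.3.6.8) is "The proportion of patients who achieve at least a partial response (PR) to therapy".
- DOR (6.3.6.2) runs "until the first date that recurrent or progressive disease is objectively documented", or to death, or otherwise to the last assessment.
- PFS (6.3.6.3) ends at relapse, progression or death.
- EFS (6.3.6.4) ends at "time of disease relapse, disease progression, alternative anti-lymphoma therapy including radiation, or death, whichever occurs first".

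Only the EFS definition mentions radiation. The reproduced response criteria (6.3.1 to 6.3.5), the evaluable populations (10.3) and the analysis section (10.4) contain no rule that excludes an irradiated lesion, closes response assessment at radiation, or censors DOR or PFS there.

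**The concern.** Local radiation is given to shrink the lesion treated. When that lesion is the only target, the dominant target or the last PET-positive site, the patient can move from stable disease to partial response (PR), or from PR to CR, for a reason unrelated to the study drugs. The definitions as written then credit the triplet. Because neither DOR nor PFS stops at radiation, the response also continues to accrue time.

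The expansion cohorts are there to give a first view of efficacy by histology (1.2.1, 10.2), and ORR and CR rate are reported by cohort and histology (10.4.3). In cohorts this small, one misattributed responder is visible in the reported rate. The CR category is also a component of complete molecular remission (6.3.6.7).

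**Working it through.** The plan states no figure that depends on radiation, so there is none to reproduce. The cohort sizes in 10.2 do add up: 18 + 6 + 12 + 6 = 42. The check has three parts.

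**1. When does the gap bite?** Take a patient irradiated on study with no progression documented beforehand.

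- Best response stays open, because 6.3.6.1 closes only at progression or recurrence.
- The patient stays evaluable, because 10.3.2 asks for measurable disease, at least one cycle and a re-evaluation.
- A later PR or CR counts under 6.3.6.8 and 6.3.6.6.
- DOR starts at that response and runs on.

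If progression was documented first, 6.3.6.1 has already closed and there is no problem.

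**2. When is the irradiated lesion decisive?** The CT-based Lugano PR in 6.3.1 needs a fall of at least 50% in the summed product of diameters (SPD) over up to six targets. Let s be the irradiated lesion's share of baseline SPD, and suppose it resolves fully. The remaining lesions must then shrink by r, where s + (1 − s)r = 0.5, so r = (0.5 − s)/(1 − s).

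| s | r needed elsewhere |
|---|---|
| 30% | 0.20/0.70 = 28.6% |
| 40% | 0.10/0.60 = 16.7% |
| 50% or more | 0% |

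A lesion with half the tumour burden therefore meets the size threshold for PR with no drug effect elsewhere. The clearest case is ocular adnexal MALT lymphoma (6.3.4), where response is judged on the lesion itself. CLL is at the other end. In 6.3.2, PR needs two of lymphocyte count, nodes and liver or spleen (relaxed if only one parameter was abnormal) plus a haematologic criterion, and CR also needs marrow and blood-count recovery. One irradiated node would rarely produce either.

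**3. How much does one patient move the rate?** The shift is 100/n, with n from 10.2.

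| Cohort | n | Shift, points |
|---|---|---|
| FL expansion | 18 | 5.6 |
| FL pooled with six dose-finding patients at the same dose | 24 | 4.2 |
| MCL expansion | 12 | 8.3 |
| MZL expansion | 6 | 16.7 (upper end) |

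For scale, assume a true count of about two-thirds responders (an assumption, not a figure from the plan). Exact 95% intervals with and without one such patient are:

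- n = 18: 12/18 = 66.7% (41.0 to 86.7) against 11/18 = 61.1% (35.7 to 82.7).
- n = 12: 8/12 = 66.7% (34.9 to 90.1) against 7/12 = 58.3% (27.7 to 84.8).
- n = 6: 4/6 = 66.7% (22.3 to 95.7) against 3/6 = 50.0% (11.8 to 88.2).

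**The case against.** The exposure is narrow. Radiation is prohibited by default and allowed only at discretion for one symptomatic lesion. A lesion that is symptomatic because it is progressing will often have closed best response already. Treatment beyond progression (3.6.1) also requires that no other treatment appears to be needed. Response is scored per patient over several sites, so most irradiated lesions would not decide the category. The endpoints are secondary, described as preliminary, and carry no test or threshold, and the intervals above overlap heavily. All of this stands. It limits the size of the problem but does not supply the missing rule.

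Four stronger readings are tempting and are not supported:

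- *That 3.7.1 contradicts 4.2.* Its sentence "Once new anti-cancer therapy has been initiated the subject will move into survival follow-up" sits under post-treatment follow-up and follows a reference to therapy started after the last dose. It does not send a patient still on study drug to survival follow-up.
- *That EFS and ORR contradict each other.* EFS is a broader composite by design, and counting radiation there but not in ORR is not in itself an error. It is also unclear whether radiation given alongside continuing study drug is alternative therapy in the sense of 6.3.6.4, so one cannot say that such a patient is certainly an EFS failure.
- *That CLL (n = 6) faces the full 16.7-point shift.* The iwCLL requirements make that close to a worst case. The same caution applies to MCL patients assessed by iwCLL (6.3) and to splenic MZL (6.3.3), where blood counts also enter.
- *That some number of the 42 expansion patients will be misclassified.* The documents give no frequency of radiation, and being irradiated is not the same as being misclassified.

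**Conclusion.** The point holds in limited form. Section 4.2 permits radiation to one lesion during treatment, and the definitions of best response, ORR, CR rate, DOR and PFS have no rule for it. Followed literally, they credit a radiation-induced response to the triplet and leave it open. That is an upward bias under the stated definitions, not merely missing detail.

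The firm figure is the effect per affected patient: 5.6 points in FL (4.2 if pooled), 8.3 in MCL and up to 16.7 in MZL, with little expected in CLL. It assumes that the irradiated lesion is decisive and that no progression was documented first. How many patients would be affected cannot be derived from the documents. The primary safety endpoint is untouched. The rule should be set before response data are analysed, because in a cohort of six a rule chosen afterwards would be made knowing its effect on the result.

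**What to change.** These changes concern analysis only; whether radiation should be allowed is a clinical matter and is not judged here.

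- **6.3.6.1, 6.3.6.6 and 6.3.6.8:** count only assessments made before any anti-lymphoma radiation towards best response, CR rate and ORR. Keep patients with no qualifying pre-radiation response in the denominator as non-responders. This needs stating because a dose-finding patient's first scheduled on-treatment scan is after Cycle 3 (Appendix G). Someone irradiated in Cycle 2 would have no earlier assessment, and dropping that patient could itself raise the ORR.
- **6.3.6.2 and 6.3.6.3:** censor DOR and PFS at the last assessment before radiation. Add a sensitivity analysis counting radiation as an event, since the censoring may be informative.
- **6.3.6.4:** state whether radiation permitted under 4.2 is an EFS event.
- **CRF:** record radiation dates explicitly. Section 4.1 lists medications and fluids and makes dates optional, although EFS already needs a radiation date.

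The cost is a few sentences and one CRF item. ORR and CR rate may come out slightly lower.

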#### 4.2.1 Venetoclax and CYP3A and P-gp Inhibitors/Inducers

##### 4.2.1.1 Venetoclax Use with CYP3A and P-gp Inhibitors

Concomitant use of venetoclax with moderate to strong CYP3A inhibitors during the ramp-up phase in MZL, MCL and CLL patients is contraindicated. Concomitant use of venetoclax with CYP3A inhibitors increases venetoclax exposure and may increase the risk for TLS at initiation and during ramp-up phase. For FL patients, moderate to strong CYP3A inhibitors are contraindicated for up to 2 weeks after initiation of venetoclax. At stable doses of venetoclax, attempts must be made to avoid concomitant use of strong or moderate CYP3A or P-gp inhibitors. However, the inhibitor may be used if needed per investigator discretion, with dose modifications as outlined in **Table 20**:

**Table 20: Management of potential venetoclax interactions with CYP3A and P-gp inhibitors**

| Inhibitors               | Ramp-Up Phase   | Patients Receiving Stable Dose of Venetoclax                      |
|--------------------------|-----------------|---|
| Strong CYP3A inhibitor   | Contraindicated | Avoid inhibitor use or reduce the venetoclax dose by at least 75% |
| Moderate CYP3A inhibitor | Contraindicated | Avoid inhibitor use or reduce the venetoclax dose by at least 50% |
| P-gp inhibitor           |                 |   |

**NOTE:** Common CYP3A and P-gp inhibitors are mentioned in [Appendix C](#).

##### 4.2.1.2 Venetoclax Use with CYP3A Inducers

Avoid concomitant use of venetoclax with strong CYP3A inducers (e.g., carbamazepine, phenytoin, rifampin, St. John's wort). Moderate CYP3A inducers (e.g., bosentan, efavirenz, etravirine, modafinil, nafcillin) may be used per investigator's discretion. Consider alternative treatments with less CYP3A induction.

## 5 CORRELATIVE STUDIES FOR RESARCH

### 5.1 BIOSPECIMEN COLLECTION

#### SUMMARY

One of the important exploratory aims of this study is to utilize multiplatform genomic analyses of tumor biopsies to identify biomarkers that predict response and/or resistance to magrolimab, both individually and in combination with venetoclax. To achieve this goal, tumor biopsies will be collected in all patients prior to therapy and optional biopsies will be obtained on patients with accessible sites of lymphoma involvement during the window period and at progression of disease. The [name] lab will perform comprehensive molecular characterization of the tumors at baseline on FFPE blocks, and this evaluation will include whole-exome sequencing, transcriptome profiling, AffySNP6.0 arrays for copy number abnormalities, and emerging technologies such as single cell RNA sequencing. Single cell RNA sequencing will be repeated on tumor biopsies obtained during the window period, and upon progression. We also plan to analyze the tumor biopsies obtained at baseline, during window period, and upon progression with histo-cytometry in [name] lab.

Blood and bone marrow samples will be collected for exploratory objectives to evaluate biomarkers of sensitivity or resistance. In blood, circulating tumor DNA (ctDNA) response and

**Abbreviated Title:** VENOM in R/R B-Cell NHL

**Version Date:** 12/18/2023

correlation with molecular tumor analysis, is planned. We will use a modern ctDNA platform that combines universal PCR primers for the variable-dense-joining (VDJ) region of the immunoglobulin receptor with next-generation sequencing (NGS) technologies (i.e., clonoSEQ®)([118](#)).

**Research Samples Calendar – Bloods:**

| Sample   | Collection Details*               | Baseline | Time Points # |             |              |               |               |  |  |                          |                                    |    | Supervising Laboratory/ Investigator |  |
|--|-----------------------------------|----------|--------------------------|-------------|--------------|---------------|---------------|--|--|--------------------------|------------------------------------|----|--------------------------------------|--|
|  |                                   |          | Window †      |             |              |               |               | Triplet Combination Therapy            |  |                          | Post-Treatment                     | PD |                                      |  |
|  |                                   |          | Cycle -2 D1              | Cycle -2 D8 | Cycle -2 D15 | Post-Cycle -2 | Post-Cycle -1 | D1 of Cycles 1, 3, 7 & 11 Δ | D1 of Cycles 1, 3, 5 & 9; Post-Cycle 12 δ | Post-Cycles 3, 6, 9 & 12 | Years 1-2= q3mos; Years 2-5= q6mos |    |                                      |  |
| cfDNA/ctDNA, Mutational panels (liquid biopsy), Plasma banking | 1 x 10 mL Streck tubes            | X        |                          | X           | X            | X             | X             |  |  | X                        | X                                  | X  | [name]                                 |  |
| Immune subsets, Protein, Immune Markers                        | 2 x 8-10 mL CPTs (sodium citrate) | X        |                          | X           | X            | X             | X             |  |  | X                        | X                                  | X  |                                      |  |
| Cytokine analysis, Serum banking                               | 1 x 10 mL in SST tube             | X        |                          | X           | X            | X             | X             |  |  | X                        | X                                  | X  |                                      |  |
| Flow cytometry   | Peripheral blood per SOC          | X        |                          | X           | X            | X             | X             |  |  | X                        | X                                  | X  | NCI LP                               |  |
| Magrolimab pharmacokinetics                                    | 1 x 3.5mL in red SST              |          | X                        |             |              |               |               | X                                      | X  |                          |                                    |    | [name]/ PPD Richmond                   |  |
| Magrolimab ADA   | 1 x 3.5mL in red SST              |          | X                        |             |              |               |               | X                                      | X  |                          |                                    |    | [name]/ PPD Richmond                   |  |

\* Tubes/media may be adjusted at the time of collection based upon materials available or to ensure the best samples are collected for planned analyses.

# All timeframes may be adjusted to similar windows as the Study Calendar ([Appendix G](#)).

† Samples from the window period will be available only for patients enrolled in dose-expansion cohorts (Cohorts 3, 4, 5 and 6).

Δ For patients in dose-expansion cohorts (Cohorts 3, 4, 5 and 6).

δ For patients in dose-finding cohorts (Cohorts 1 and 2).

**NOTE:**

- All blood samples/tubes should remain at ambient temperature after collection and processed on the day of collection; do not place samples on ice unless otherwise instructed.
- Subjects who discontinue treatment for a reason other than disease progression and who do not start new treatment should continue to have samples collected at the scheduled time points.

**Research Samples Calendar – Tissue/Other:**

| Sample  | Collection Details*  | Time Points  | Supervising Laboratory/
Investigator |
|---|--|--|---|
| Tissue Samples                                   |  |  |   |
| Archival and/or Fresh Tissue Biopsy                     | 
 
FFPE (block or slides); biopsy is required if archival is not adequate or unavailable
 
Excision (single or multiple nodes) or core (6 passes); placed in formalin/FFPE and media, as appropriate
 
 | 
 
Baseline; if required for adequate tissue
 
During 1st cycle (Cycle -2; preferably day 8) of doublet therapy with magrolimab + obinutuzumab in window period (optional)†
 
At disease progression/end of treatment
 
   | [name], [name],
NCI LP              |
| Tissue/Imaging Analyses                                 | No additional tissues or imaging will be performed for these analyses, only use of already collected samples and/or imaging, as described in Section 5.3.6   |  | [name]                                  |
| Other Samples                                    |  |  |   |
| Germline DNA  | 
 
Blood, Buccal swab, or Saliva (preferred)
 
  | 
 
Baseline
 
   | [name]                                    |
| Bone marrow aspirate ( $\pm$ flow cytometry) and biopsy | 
 
Aspirate (<math>\pm</math> flow cytometry) (SOC; heparinized tubes or EDTA/sodium heparin or formalin, as appropriate)
 
Biopsy (SOC; formalin or no media, as appropriate)
 
                       | 
 
Baseline
 
During 1st cycle of doublet therapy with magrolimab + obinutuzumab (Cycle -2; preferably day 8) in window period (optional)†
 
At disease progression or suspicion of CR
 
After Cycle 6 of triplet therapy (magrolimab + obinutuzumab + venetoclax) in patients with involvement at baseline. For patients with no baseline bone marrow involvement, biopsy may be performed per investigator's discretion.
 
 | [name],
NCI LP\                        |

\*Tubes/media may be adjusted at the time of collection based upon materials available or to ensure the best samples are collected for planned analyses.

†Samples from the window period will be available only for patients enrolled in dose-expansion cohorts (Cohorts 3, 4, 5 and 6)

**NOTE:**

- All samples/tubes should remain at ambient temperature after collection and processed on the day of collection; do not place samples on ice unless otherwise instructed.
- Subjects who discontinue treatment for a reason other than disease progression and who do not start new treatment should continue to have samples collected at the scheduled time points.

## **5.2 SAMPLE COLLECTION AND PROCESSING**

### **5.2.1 Summary**

The planned analyses described below may be done on leftover and/or shared sample portions from the respective laboratories, as needed. In addition to the prospectively collected samples below, leftover portions of samples sent for routine laboratory testing (e.g., plasma from CBC/other hematology labs) may also be retrieved for research tests prior to being discarded. The planned prospective analyses are identified below; laboratories may share resources or collaborate on analyses, if appropriate (e.g., isolation/analysis of DNA not prospectively planned by one lab may be incorporated if needed during the planned analyses).

Portions of all samples may be banked for future research analyses; prospective consent will be obtained during the informed consent process.

